
Sample Size The precise sample size for the study has not been pre-specified, but is expected to lie between 12,000 and 20,000 study participants depending on the ratio of patients with a prior vertebral fracture to those without a prior vertebral fracture who

Product: MK-0822

4

Protocol/Amendment No.: 018-04

enroll in the study. According to data obtained from participating investigational sites 'Lead Cohort', the anticipated ratio of patients with a prior vertebral fracture to those without a prior vertebral fracture is approximately 1:3. Based on the overall fracture risk of this mixed population, the sample size is predicted to be approximately 16,300, comprised of approximately 4100 patients with a prior vertebral fracture and approximately 12,200 patients without a prior vertebral fracture. The size of the sample may be revised downward if a higher than anticipated proportion of patients with a prior fracture is enrolled. Conversely, it may be revised upward if a lower than expected proportion of patients with prior fracture is enrolled, or if additional exposure to assess safety is desired.

Trial Duration The study is expected to be approximately 5 years in duration, including 1 year for enrollment, and is not anticipated to exceed a total of 4 years duration for study participants in the 'Main Cohort'. For those in the 'Lead Cohort', trial duration could be approximately 5 years. Interim analyses will be performed after approximately 70% and 85% of hip fracture events have occurred so as to retain the possibility of early trial termination for efficacy (see Data Analysis Section 3.5.5.6). Patients will be monitored for excessive bone loss throughout the study. Those patients determined to have excessive bone loss will be discontinued from the blinded study therapy for treatment with available therapy.

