Two height measurements will be taken and recorded on the eCRF. If the 2 measurements differ by 4 mm or more, a third and fourth measurement will be obtained and recorded on the eCRF. The mean of the last 2 measurements will be used as the estimate of stature.

Change from baseline in stature at each of the yearly timepoints will be secondary endpoints. The number (percentage) of patients with a stature loss of greater than 1 cm during the study will also be analyzed, as will the rate of stature loss.

Height measurements performed on non-calibrated stadiometers or otherwise not obtained according to protocol procedures will be excluded from the analyses. Details on the criteria for exclusion from analysis will be documented in a memo before unblinding the team for the final analysis.

Secondary Bone Mineral Density Endpoints

The percent change from baseline in BMD measurements at the lumbar spine, total hip, femoral neck, trochanter, and 1/3 distal forearm will also be secondary endpoints. BMD measurements will be performed at baseline and each of the yearly timepoints.

For the lumbar spine (posterior/anterior [PA] view) measurements, mean BMD values from at least three evaluable vertebrae (four when available) from L1 to L4 will be used. If a vertebra becomes fractured during the study or was fractured at baseline, BMD data for this vertebra will be excluded from all analyses.

For the hip BMD measurement, the side of the hip measured must be consistent throughout the entire study. If the hip side that is being measured becomes fractured during the study, then data of that hip side will be excluded from the time of the fracture onward.

All analyses of BMD efficacy endpoints will incorporate the longitudinal BMD correction factor as determined by a single quality control center.

Product: MK-0822

44

Protocol/Amendment No.: 018-04

BMD at the total body and 1/3 distal forearm will only be performed in a random 10% subset of the randomized patients, identified by the IVRS system

Biochemical Markers of Bone Resorption and Bone Formation

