A similar FAS population will be used as the analysis approach for BMD endpoints and stature, including all randomized patients who took at least one dose of study medication and have the necessary on-treatment information. Missing data will be handled by the longitudinal model, therefore no imputation of missing data will be necessary. As indicated in appendix 6.7, BMD measurements taken more than 30 days after the last dose of study medication will primarily not be included in the analyses, for results to be consistent with those from phase IIb and future phase III studies. For consistency with the approach for fracture endpoints, a supportive analysis including these measurements taken long after the last dose will also be performed.

The analyses of biochemical markers of bone turnover and formation will be performed using the per-protocol approach. BMD at the total body and distal forearm and biochemical marker endpoints will only be performed for approximately 10% of the randomized patients.

Time to first major cardiovascular and cerebrovascular event will be handled similarly as clinical fractures and will be based on the FAS approach.

Summary tables for health resource and meal questionnaires and bone biopsies will be for the FAS population.

Safety analyses will be based on the "All-Patients-as-Treated" (APaT) population, which includes all randomized patients who received at least one dose of study medication. For safety analyses, patients will be included in the treatment group for the treatment they actually received. For safety analyses, missing data will not be imputed.

Product: MK-0822

47

Protocol/Amendment No.: 018-04

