In addition, the percentage of patients who experienced a stature loss of greater than 1 cm during the study will be tabulated. A logistic model will be used to compare the two treatment groups, including terms for treatment, geographic region and stratum. The model-based odds ratio, and 95% confidence interval, will be provided as an estimate of the treatment effect.

The rate of stature loss will also be examined, using a mixed model with fixed effects for treatment, geographic region, stratum, treatment-year interaction and random intercept and slope (year). The within patient serial correlation of the values over time will be modeled by an unstructured covariance matrix. The magnitude of the slopes (rate of stature loss) will be summarized from the model, as well as the difference between treatments (mean and 95% CI). More detail on this mixed model is in appendix 6.7.

Bone Mineral Density Endpoints

For each body site and timepoint, BMD will be summarized at baseline and follow-up, by the mean and standard error, together with the mean percent change from baseline and its 95% confidence interval.

The percent change from baseline in BMD endpoints at all during-treatment time points will be analyzed using a longitudinal model with fixed effects for treatment, stratum, geographic region, and treatment-by-time interaction¹. The within patient serial correlation of the values over time will be modeled by an unstructured covariance matrix. More detail on this longitudinal model is in appendix 6.7.

The treatment effect at each of the on-treatment time points will be assessed by evaluating the within- and between-treatment group Least-Squares means (LS mean) and the associated 95% confidence intervals. Treatment difference will be tested at each of the on-treatment time points and adjustment for multiple testing will be handled as discussed below.

Similar analyses will be performed in the subgroup of bisphosphonate-intolerant patients (defined as patients with a contraindication or history of intolerance to bisphosphonates, or those considered by their physician to be unsuitable for bisphosphonate treatment).

A graphical presentation of the LS mean (+/-SE) change from baseline over time will also be provided.

Biochemical Markers

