3.5.5.4 Sample Size and Power Calculations

Underlying Assumptions

Sample size estimates are based on estimates of fracture incidence rates from the Fosamax Fracture Intervention Trial (FIT) data. It is assumed that the expected relative risk (RR) for morphometric vertebral fractures is 0.5, for non-vertebral fractures 0.8 and for hip fractures 0.65². Sample sizes are based on a 4% alpha level at the final analysis (to account for the interim analyses, see multiplicity adjustment section, the final alpha will be $\geq 4\%$) and 90% power.

To ensure enrollment of a study population with adequate overall fracture risk it was decided to have a flexible sample size depending on the observed ratio of number of patients with a prior vertebral fracture to number of patients without prior vertebral fracture. It is expected that the total sample size needed will be smaller if more patients with a prior vertebral fracture can be included.

For the sample size calculations it is assumed that the recruitment period will be approximately 1 year and the total study duration (including the recruitment period) will be approximately 5 years. Other assumptions used to derive the different scenarios are based on estimates from the FIT data and are detailed in Table 3-12.

² In a recent study of the Novartis compound (ASBMR 28th annual meeting -sep 2006 - S16. Abstract #1054 D. Black et. al.) the relative risk for hip fractures was 0.6.

Product: MK-0822

61

Protocol/Amendment No.: 018-04

Table 3-12

Underlying Assumptions Used for Calculations of Sample Size, Based on FIT Data

Patient Population / Fracture Type	Approximate Placebo Fracture Rate	Relative Risk	Drop-out Rate
Patients with no prior vertebral fracture			
Vertebral fractures	4% at 2 years	0.5	10% with no data at all
Hip fractures	1.4% at 3 years	0.65	20% over 3 years
Non-vertebral fractures	8% at 2 years	0.8	13% over 2 years
Patients with 1 prior vertebral fracture			
Vertebral fractures	8% at 2 years	0.5	10% with no data at all
Hip fractures	3% at 3 years	0.65	20% over 3 years
Non-vertebral fractures	11% at 2 years	0.8	13% over 2 years

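### The comparison of height loss over 1 cm ignores time observed, so its odds ratio is biased if the arms stop treatment at different rates

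*Protocol*

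**What the plan says.** Section 3.5.3 lists the endpoint: "The number (percentage) of patients with a stature loss of greater than 1 cm during the study will also be analyzed". Section 3.5.5.1 (Stature) repeats that "the percentage of patients who experienced a stature loss of greater than 1 cm during the study will be tabulated", gives the model as "A logistic model will be used to compare the two treatment groups, including terms for treatment, geographic region and stratum", and adds "The model-based odds ratio, and 95% confidence interval, will be provided as an estimate of the treatment effect". No time point is fixed, and the model contains neither follow-up time nor visit.

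Section 3.5.4 defines the analysis set for BMD and stature as "including all randomized patients who took at least one dose of study medication and have the necessary on-treatment information". Its only missing-data rule for these endpoints is "Missing data will be handled by the longitudinal model, therefore no imputation of missing data will be necessary".

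Table 3 of Appendix 6.7, which covers BMD and height, admits a measurement to the main analysis only if it falls within 30 days of the last dose. Its footnote adds a supportive analysis with no such limit. The running text of 3.5.4 states the 30-day rule for BMD alone; Table 3 is where it reaches height.

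Section 3.5 says that the details of the stand-alone analysis plan are already incorporated in the protocol, so this specification is meant to be complete.

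**The concern.** A woman whose last usable height is at Month 12, with no 1 cm loss by then, is scored the same as a woman followed for four years without such a loss. The longer a woman is measured, the more chance she has to cross the threshold. If one arm is measured for less time on average, it shows fewer losses for that reason alone.

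The arms could differ here. Section 3.2.3.9.1 stops blinded therapy for several reasons that may depend on treatment, among them a 7% BMD loss, which could plausibly fall more on placebo. Adverse experiences could act the other way. Women who stop are still followed off drug, but Table 3 removes their later heights from the main analysis.

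The missing-data sentence in 3.5.4 fits the height-slope mixed model and the BMD models. It gives the logistic model nothing. Elsewhere the plan does allow for time: a grouped-time model for morphometric vertebral fractures, Cox models for clinical fractures, and patient-years for Tier 1 adverse experiences.

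At stake is a treatment estimate for height that partly measures follow-up.

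**Working it through.** **Plan figures.** The protocol gives no rate, effect size or power for height loss, so there is no planned figure to reproduce. Table 3-12 assumes hip-fracture drop-out of "20% over 3 years", equal in both arms. With the exponential drop-out of 3.5.5.4 this means 1 − 0.80^(2/3) = 13.8% at 2 years (the table has 13% for non-vertebral fractures) and 1 − 0.80^(4/3) = 25.7% at 4 years. I use 20% only as a stand-in for loss of usable heights.

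**Closed-form check with no treatment effect.** Assume a constant hazard λ of first loss over 1 cm, exponential stopping at rate μ unrelated to height, follow-up of at most 4 years, and a height at exit. Then

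P(loss observed) = λ/(λ+μ) × [1 − exp(−4(λ+μ))].

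Take an assumed 3-year loss rate of 40%, with 3-year stopping of 20% on placebo and 25% on odanacatib:

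- λ = −ln(0.60)/3 = 0.1703
- μ = −ln(0.80)/3 = 0.0744 (placebo) and −ln(0.75)/3 = 0.0959 (odanacatib)
- P = 0.434 (placebo) and 0.419 (odanacatib)
- odds ratio = (0.419/0.581)/(0.434/0.566) = 0.94, although the true effect is nil.

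For assumed loss rates of 20%, 40% and 60%, the odds ratio is 0.95, 0.94 and 0.92. At 8,150 per arm (16,300/2), a two-sided 5% test then rejects in 26%, 51% and 75% of trials. With annual heights only, the rejection rates are 15%, 29% and 45%. With equal stopping the odds ratio is 1.00 and rejection stays at 5%.

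**Simulation with a treatment effect.** All inputs are assumed: mean loss 2.0 mm/year on placebo and 1.6 on odanacatib, between-woman SD 2.5 mm/year, measurement SD 3 mm, annual heights, 3 to 4 years planned, and stopping independent of height loss. Women with no on-treatment height are excluded, as 3.5.4 requires.

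| Loss of usable heights over 3 years | Odds ratio |
|---|---|
| None | 0.79 |
| 20% in both arms | 0.81 |
| 25% placebo, 20% odanacatib | 0.85 |
| As above, plus bone-loss stops 5% v 1% | 0.88 |
| As above, with bone-loss stops 10% v 1% | 0.91 |

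These figures move by about 0.01 with how study closure is modelled. In the last row z is about −2.7 at 8,150 per arm. The grouped-time complementary log-log hazard ratio is 0.84 throughout. It is on a different scale from the odds ratio, so the comparison that matters is that it does not move.

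**Same simulation with no effect.** The odds ratio is 1.00 with equal stopping, 1.05 at 25% placebo v 20%, 0.95 with that imbalance reversed, and up to 1.13 with the bone-loss stops. The complementary log-log hazard ratio is 1.00 in each case.

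**The case against.** Several stronger readings are tempting, and the documents do not support them.

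- *Every early leaver counts as a success.* No. Section 3.5.4 excludes a woman with no on-treatment height; only those with at least one usable height and no observed loss are scored as no loss. End-of-study procedures at discontinuation (3.2.3.9) should also give many leavers an exit height.
- *Drop-out of 20%, or the different lengths of the two cohorts, biases the result.* Section 1.4 does say "For those in the 'Lead Cohort', trial duration could be approximately 5 years", against about 4 years for the Main Cohort, but randomization balances cohort and closure date. They blur what the percentage means without biasing the comparison. Equal stopping barely moves the odds ratio. Every imbalance used above is assumed.
- *The bias runs toward no effect because placebo stops more.* That is plausible through the bone-loss rule but not established. More stopping on odanacatib would flatter the drug.
- *Nothing in the plan covers the women stopped for bone loss.* They remain in follow-up, and the supportive analysis in Table 3 restores their off-drug heights. This is a real mitigation, though that analysis is secondary and the logistic model in it would still ignore time.
- *A confirmatory test is at risk.* Stature is in a formally tested secondary family (3.5.5.3), but that testing steps down over time points, which a single whole-study yes/no cannot enter. Section 3.5.3 names yearly change from baseline as the secondary endpoint, and the odds ratio is never named as the confirmatory height test.

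The height-slope model already uses follow-up time. Nor is the alternative immune. If bone-loss stopping is related to height loss (assumed correlation 0.3 to 0.5), the complementary log-log hazard ratio drifts to between 0.84 and 0.87.

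**Conclusion.** The point holds within limits. Followed as written, the logistic comparison of height loss over 1 cm makes no allowance for time observed, the missing-data rule does not reach it, and Table 3 ends height observation 30 days after the last dose. Unequal stopping therefore biases the odds ratio in favour of the arm that stops sooner. The direction is unknown in advance, and equal stopping leaves almost no bias. In the simulation, the shift is from 0.79 to between 0.85 and 0.91 when placebo stops more, and from 1.00 to somewhere between about 0.95 and 1.13 with no true effect. These sizes rest on assumed height-loss rates, assumed imbalances and stopping unrelated to height loss. The primary endpoints are unaffected, and the slope model and the all-data supportive analysis partly mitigate the flaw. It is worth correcting because the correction is cheap.

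**What to change.** Analyse first observed height loss over 1 cm by annual visit, using the complementary log-log grouped-survival model already written out in Appendix 6.7 for morphometric vertebral fractures, with terms for treatment, period, stratum and region. Censor each woman at her last usable height. Report life-table percentages by year in place of the crude percentage, and keep the logistic model as descriptive. Run the same time-based model in the supportive analysis that includes off-drug heights, and say in the text of 3.5.4 that the 30-day rule applies to height.

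The cost is a few sentences and re-use of existing code. The effect would be reported as a hazard ratio instead of an odds ratio. The model assumes non-informative censoring, which bone-loss stops may violate; the supportive run with off-drug heights is the check on that.

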Analysis of log-transformed fraction of baseline value in biochemical markers of bone resorption (s-CTX, u-NTx) and bone formation (s-BSAP, s-P1NP) will utilize the same longitudinal model as BMD endpoints. The means and the associated 95% CIs will be back-transformed for presentation and the delta method will be used to back-transform

¹ The protocol (018-00) foresaw a random intercept in the model. Due to the unstructured covariance matrix, the random intercept is redundant and therefore omitted from the model.

Product: MK-0822

50

Protocol/Amendment No.: 018-04

the between-treatment difference (in weighted LS means) and 95% confidence interval. Formal testing of treatment differences will only be performed for resorption markers. A graphical presentation of the weighted LS mean (+/-SE) change from baseline (after back-transformation) over time will also be provided, as well as a graphical presentation of the mean actual values over time by treatment. Formal testing of treatment differences will only be performed for resorption markers.

Indices of calcium and mineral homeostasis will be summarized in similar fashion to biochemical markers, and no statistical testing will be performed to compare the treatment groups.

In addition, frequency tables will be provided for the percentage of patients with 25-hydroxyvitamin D levels <9 , ≥ 9 to <20 , or ≥ 20 ng/mL at baseline and at Month 12.

Bone Biopsies

The 2-D Histomorphometry and 3-D μ -CT transilial bone biopsy measurements at Month 24 and 36 will be summarized (mean, standard error and 95% CI) for each of the treatment groups. The principle purpose of these analyses is to rule out an increased incidence of qualitative abnormalities (e.g. excessive osteoid, woven bone, mineralization defect, marrow fibrosis), the number (percent) of patients with a qualitative abnormality will therefore be summarized for both treatment groups, along with the Miettinen and Nurminen method [23] based 95% confidence interval on the difference in percentage. The incidence of qualitative abnormalities on the bone biopsies will be considered a safety endpoint rather than an efficacy endpoint.

Meal and Health Resource Utilization Questionnaires

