In the interim analyses, the trial will not be terminated unless strong evidence (significance) is seen for all 3 primary fracture endpoints, more detail is provided below.

Multiplicity Adjustment for Secondary Endpoints

Secondary efficacy endpoints include clinical vertebral fractures, stature, BMD measures at different sites, and biochemical markers of bone resorption. Statistical significance for the secondary endpoints will only be considered if the treatment difference for the first primary endpoint (morphometric vertebral fractures) was significant. It is recognized that this does not account for the presence of multiple primary endpoints, but it is felt that this approach is clinically meaningful and acceptable.

For the purpose of addressing the issue of multiplicity due to multiple secondary endpoints, BMD measurements at the total hip, femoral neck, trochanter, lumbar spine, and distal forearm will be considered one family. Biochemical markers of bone resorption (s-CTX, u-NTx) will be considered a second family and clinical vertebral fractures and stature a third family. Within each family a Hochberg [8] multiplicity adjustment procedure will be used to ensure a family-wise type I error rate of 5% within each of the families (conditional on significance at later time points for BMD and height and conditional on significance at earlier time points for biomarkers). No adjustment for multiplicity across the families will be applied.

For BMD and height, a step-down procedure will be used to account for the multiplicity over time, starting from the last time point to the earliest time point where no significant conclusion can be claimed. At earlier time points significance will only be claimed if there was significance at the later time points and if from the Hochberg procedure including all other endpoints significance can be concluded, as explained in [24]. Since the very last timepoint in the study may be obtained only for a limited number of patients, the last timepoint which was performed for at least 50% of the patients will be taken as the last time point in this multiplicity adjustment strategy and the later time point(s) will be considered exploratory.

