1:3	1.8	0.6	20%	169	12,150	9,100	3,050
1:2	1.9	0.6	20%	168	11,300	7,550	3,750
1:1	2.2	0.6	20%	168	9,900	4,950	4,950

Power for Vertebral and Non-vertebral Fractures and BMD

All sample size calculations above are based on the estimates for the hip fracture incidence, since the analyses for morphometric vertebral and non-vertebral fractures have more power than those for hip fractures. For example, if 4,100 patients with one prior vertebral fracture and 12,200 patients without a prior vertebral fracture are randomized into the trial (see Table 3-13), there will be >99% power to detect a treatment difference in morphometric vertebral fractures and in non-vertebral fractures, using the assumptions of Table 3-12 and a significance level of 0.04.

With a total of at least 12,000 patients, there will be >99% power to detect a clinically meaningful BMD difference. For example, assuming that there are 6,000 patients per group, the common standard deviation (SD) is 4%³, alpha is 5% and power of 99% the minimal detectable difference is 0.3%. When 1,200 (10%) patients have a BMD measurement (for distal forearm and total body), a 1% difference can be detected with 99% power ($\alpha=5%$, SD=4%).

Note on Hochberg Procedure

As detailed in Section 3.5.5.3, a combination of a step-down and Hochberg procedure will be used to account for multiplicity due to multiple primary endpoints. This means that if the p-value for non-vertebral fractures is $>\alpha$, hip fractures need to be tested at $\alpha/2$. Similarly, if the p-value for hip fracture is $>\alpha$, then non-vertebral fractures need to be

³ The estimated 4% standard deviation was obtained from the phase IIb study and previous alendronate studies.

Product: MK-0822

64

Protocol/Amendment No.: 018-04

tested at $\alpha/2$. The actual alpha of the final analysis is detailed in Section 3.5.5.6 and will be between 4% and 5%.

To get some idea of the loss in power, the raw powers (not taking multiplicity adjustments or correlations between endpoints into account) for hip and non-vertebral fractures at 2% significance level are also calculated.

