Where “stature” is the stature, “an” is the allocation number, “trt” is the treatment group (“Placebo”, ”MK-0822 50 mg”), “year” and “yearc” are the numerical value of the year defined by the time windows in below, “stratum” is the stratum (prior/ no prior vertebral fracture), and “region” is the geographic region.

Longitudinal Models for BMD

To assess the treatment effect over time a longitudinal analysis will be conducted including data of all time points. In this analysis, the percent change from baseline in lumbar spine BMD at all during-treatment time points will be analyzed by means of a mixed model (SAS proc mixed) including fixed effects for treatment, stratum, geographic

Product: MK-0822

24

Protocol/Amendment No.: 018-04

region, and treatment-by-time interaction, as well as a random intercept for each patient. The within patient serial correlation of the values over time will be modeled by an unstructured covariance pattern. The FAS approach will be used in this analysis and no last-observation-carry-forward will be applied to the data. Estimates of the difference between MK-0822 and placebo at each time point will be provided from this model.

The above model will be fit using the following SAS PROC MIXED statement:

```
proc mixed method = reml data = <dataset> order=internal;

  class an trt region month stratum;

  model percent_change = trt stratum region trt*month / s ddfm=kenwardroger;

  repeated month / type = UN subject = an r rcorr;

  lsmeans trt trt*month / cl pdiff om;

run;
```

Where “percent_change” is the percent change from baseline in lumbar spine BMD, “an” is the allocation number, “trt” is the treatment group (“Placebo”, ”MK-0822 50 mg”), “month” is the month defined by the time windows below, “stratum” is the stratum (prior/ no prior vertebral fracture), and “region” is the geographic region.

The same approach will be used for the other BMD endpoints.

The weighted LS means, weighted for region and stratum size, using the OM option in SAS proc mixed, will be primarily used to summarize and plot the percent change from baseline within treatment groups at each timepoint.

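### The longitudinal models for BMD and bone markers leave out the patient's baseline value; the analysis is valid but gives up some precision, mainly for the resorption markers

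*Protocol*

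**What the plan says.** For BMD, Section 3.5.5.1 states: "The percent change from baseline in BMD endpoints at all during-treatment time points will be analyzed". The method is a "longitudinal model with fixed effects for treatment, stratum, geographic region, and treatment-by-time interaction" with an unstructured within-patient covariance. The code in Appendix 6.7 has the same terms: "model percent_change = trt stratum region trt*month / s ddfm=kenwardroger". For bone markers, the analysis of the log fraction of baseline "will utilize the same longitudinal model as BMD endpoints".

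These models carry formal tests. For BMD, "Treatment difference will be tested at each of the on-treatment time points", and Section 3.5.5.3 says that "BMD measurements at the total hip, femoral neck, trochanter, lumbar spine, and distal forearm will be considered one family" under Hochberg. For markers, "Formal testing of treatment differences will only be performed for resorption markers"; these are s-CTX and u-NTx, which form their own Hochberg family. The formation markers share the model but are not tested.

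Markers and distal forearm BMD are measured only in a random 10% subset, and the marker analysis uses the per-protocol set (Section 3.5.4). Sections 3.5 and 6.7 both say that the detail of the separate SAP has been absorbed into the protocol, so on the document's own account this is the full model specification.

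**The concern.** Both endpoints are change scores, and a change score is generally correlated with its own baseline. Leaving baseline out keeps that predictable variation in the residual. It also lets a chance difference in baseline between arms pass into the treatment difference. Nothing elsewhere in the model compensates: the response holds only during-treatment values, whereas the stature slope model in Appendix 6.7 includes the baseline heights in its response.

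At stake is the width of the confidence intervals on the LS-mean differences, most of all where numbers are smallest. The marker models have the most to gain. Besides the 10% subset, the per-protocol rules in Appendix 6.7 drop patients or values for post-randomisation reasons (missed doses, low compliance, concomitant bone drugs, time since last dose). Baseline balance in that set is therefore not secured by randomisation alone.

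**Working it through.** **1. The plan's own power figures.** Section 3.5.5.4 works by "assuming that there are 6,000 patients per group, the common standard deviation (SD) is 4" (percent). I take a two-sided test and 1:1 allocation.

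- 6,000 per group, alpha 5%, power 99%: detectable difference = (1.960 + 2.326) × 4 × √(2/6,000) = 0.313%. The plan says 0.3%.
- 600 per group (10% subset), 1% difference: standard error = 4 × √(2/600) = 0.231, and power = Φ(1/0.231 − 1.960) = 99.1%. The plan says 99%.
- 1,400 per group (bisphosphonate-intolerant), 1% difference, alpha 4.5%: power is above 99.9%. The plan says above 99%.

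All three reproduce.

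**2. What a baseline term would gain.** Let r be the within-patient correlation of baseline with follow-up, and let both have SD s.

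- Variance of the change: 2(1 − r)s².
- Residual variance after adjusting for baseline: (1 − r²)s².
- Ratio: (1 + r)/2, so the reduction is (1 − r)/2.

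The log fraction of baseline is a difference of logs, so the formula fits the markers directly. For percent change in BMD it is only an approximation. The protocol does not give r; the values below are assumptions.

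| r | Variance reduction | CI narrower by | Equivalent extra patients |
|---|---|---|---|
| 0.50 (marker) | 25% | 13.4% | 1/0.75 = 33% |
| 0.70 (marker) | 15% | 7.8% | 1/0.85 = 18% |
| 0.90 (BMD) | 5% | 2.5% | 1/0.95 = 5% |
| 0.95 (BMD) | 2.5% | 1.3% | 1/0.975 = 3% |

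A single-visit simulation (600 per arm, 2,000 replicates) gave adjusted/unadjusted standard error ratios of 0.88, 0.91 and 0.99 at r = 0.5, 0.7 and 0.95. Theory gives 0.87, 0.92 and 0.99.

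Without the equal-SD assumption, the reduction is c², where c is the correlation of baseline with the change. Over |c| = 0.1 to 0.6 (assumed) it runs from 1% to 36%.

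**3. Size of the subset.** Section 3.1.1.1 reports 16,716 enrolled; 10% of that over two arms is about 836 per arm. This is an upper figure for markers, before the per-protocol exclusions.

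**4. Effect on BMD power.** Take |c| = 0.2, a 4% variance reduction. Power for 1% at 600 per group moves from 99.1% to 99.3%. If only half of the subset reaches the time point that starts the step-down (300 per group, the floor of the 50% rule in Section 3.5.5.3), it moves from 86.5% to 87.8%.

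**5. Scanner scale.** Inclusion criterion 2 puts a femoral neck T-score of −2.5 at 0.558 (Hologic), 0.691 (GE Lunar) and 0.629 g/cm² (Norland). The Hologic–Lunar gap is 0.133, more than one T-score unit on Hologic (0.678 − 0.558 = 0.120). Raw baseline BMD pooled over makes would be a noisy covariate.

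**The case against.** The strongest reply is that nothing here is wrong. Under randomisation the unadjusted difference is unbiased, and its standard error already allows for chance imbalance. That stands, and it makes this a point about efficiency. It is somewhat weaker for the per-protocol marker set, but a baseline term there corrects only for the baseline value itself, not for selection in general.

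A reader might infer that the secondary tests are underpowered or that a conclusion hangs on the missing term. The documents do not support this. The plan's power for a 1% BMD difference is 99% or more in the full sample, the 10% subset and the bisphosphonate-intolerant subgroup. Section 3.1.5 reports BMD gains from baseline of 5.5% and 3.8%, and resorption-marker suppression of roughly 60% to 70%. The 300-per-group case is a floor, and under Hochberg the forearm is tested at the full alpha if the other four sites succeed.

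The BMD gain may be smaller still. Entry criteria restrict hip baseline, and stratum, which has its own T-score threshold, is already in the model. If selection halved the baseline SD (an assumption), the reduction at r = 0.90 would be (0.10² × 0.25)/(0.10² × 0.25 + 0.19) = 1.3% instead of 5%. Percent change is also free of scanner scale, which is a fair reason for choosing it as the endpoint. It is no reason to omit a standardised baseline covariate.

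**Conclusion.** The omission is real and consistent between text and code, and the document gives no reason for it. The loss is modest. For the two formally tested resorption markers, the variance could fall by about 15% to 25%, assuming r between 0.5 and 0.7 and equal spread on the log scale. For BMD it is probably 5% or less. Neither correlation can be derived from the protocol.

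It would go too far to call the present analysis biased, to say that a stated power figure fails, or to extend the point about formal testing to the formation markers. It would also be wrong to treat raw baseline BMD as a cost-free covariate. Low severity: worth doing because it is cheap.

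**What to change.** In Section 3.5.5.1 and the code in Appendix 6.7:

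- **Markers:** add log baseline marker and its interaction with time, for example `model log_fraction = logbase logbase*month trt stratum region trt*month`.
- **BMD:** add baseline T-score for the site analysed and its interaction with time, or baseline BMD together with machine type. Do not use raw BMD pooled over makes. Appendix 6.7 already plans to summarise baseline BMD by machine type and baseline T-scores.

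The cost is one parameter per post-baseline visit (five for markers at Months 6, 12, 24, 36 and 48) and, for BMD, the need to standardise by machine. No patient is lost, because the endpoint cannot be computed without a baseline. The change should be fixed before unblinding; Section 3.5 allows for amending important secondary analyses. The same edit can settle the Appendix 6.7 text on the BMD model, which still describes a random intercept that the footnote in Section 3.5.5.1 says was dropped and the code does not contain.
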